3.2. Safety Objectives and Endpoints

Objectives	Endpoints
To characterize the safety of treatment with fordadistrogene movaparvovec as compared to placebo.	
Incidence, severity and causal relationship of treatment-emergent AEs (TEAEs) (AEs and SAEs) through Week 52.
 
Incidence of abnormal laboratory findings and magnitude of change through Week 52.
 
Abnormal and clinically relevant changes through Week 52 in:
 
 • Physical exam; • Neurologic exam; • Weight; • Vital signs; • ECG; • Echocardiogram; • Cardiac MRI • Child Behavior Check List (CBCL).

Objectives	Endpoints
To characterize the safety of treatment with fordadistrogene movaparvovec in participants in Cohort 2.	
Incidence, severity and causal relationship of TEAEs (AEs and SAEs) after fordadistrogene movaparvovec administration through Year 2 Week 52.
 
Incidence of abnormal laboratory findings and magnitude of change from pre-fordadistrogene movaparvovec baseline through Year 2 Week 52.
 
Abnormal and clinically relevant changes from pre-fordadistrogene movaparvovec baseline through Year 2 Week 52 in:
 
• Physical exam;• Neurologic exam;• Weight;• Vital signs;• ECG;• Echocardiogram;• Cardiac MRI• CBCL.
To characterize the long-term safety of treatment with fordadistrogene movaparvovec.	
Incidence, severity and causal relationship of TEAEs (AEs and SAEs) through 5 years post fordadistrogene movaparvovec administration.
 
Incidence of abnormal laboratory findings and magnitude of change through 5 years post fordadistrogene movaparvovec administration.
 
Abnormal and clinically relevant changes through 5 years post fordadistrogene movaparvovec administration in:
 
• Physical exam;• Neurologic exam;• Weight;• Vital signs;• ECG;• Echocardiogram;• Cardiac MRI• CBCL.

4. STUDY DESIGN

4.1. Overall Design

This is a Phase 3, global, multi-center, randomized, double-blind, placebo-controlled study to assess the safety and efficacy of fordadistrogene movaparvovec gene therapy in approximately 99 ambulatory male participants (in the FAS; see [Section 9.3](#)), ages ≥ 4 to < 8 years, with a genetic diagnosis of DMD who are on a stable daily regimen of glucocorticoids.

Eligible participants will be randomized into Cohort 1 or Cohort 2 in a 2:1 fashion and stratified by their age at Screening (< 6 or ≥ 6 years old). Study enrollment will be managed to ensure that no more than approximately 55% of dosed participants are in either of the Screening age strata. Enrollment will be assessed periodically, and if an imbalance is noted, enrollment of the overrepresented stratum may be paused until a more balanced distribution is achieved. In the context of this study, treatment will consist of two single intravenous infusions, one of fordadistrogene movaparvovec and one of placebo, with the timing and sequence as described below:

- Cohort 1 (approximately 66 participants): will receive a single dose of fordadistrogene movaparvovec on Day 1 (Visit 3) and a single dose of placebo at Day 390 (Visit 20). They will be followed for 5 years after the administration of the single dose of fordadistrogene movaparvovec. Total time on study will be approximately 5 years.
- Cohort 2 (approximately 33 participants): will receive a single dose of placebo on Day 1 (Visit 3) and a single dose of fordadistrogene movaparvovec at Day 390 (Visit 20), if they remain eligible. They will be followed for 5 years after the administration of the single dose of fordadistrogene movaparvovec. Total time on study will be approximately 6 years.

In order to ensure an adequate understanding and management of potential safety risks, the initial rate of randomization into the study will be limited. No more than 2 participants per week will be randomized at the start of the study, until 4 participants have been observed for at least 2 weeks post-IP administration. After that, the rate could be increased to no more than 3 participants randomized per week (until a total of 10 participants have been observed for at least 2 weeks post-IP administration). Thereafter, the rate of randomization could be further increased to no more than 5 participants randomized per week (until a total of 20 participants have been observed for at least 2 weeks post-IP administration). After this time, no limits to the randomization rate will be imposed unless the study team, in consultation with the E-DMC, determines otherwise. Ongoing blinded review of safety data will be conducted by the study team, and frequent periodic unblinded reviews of safety data will be conducted by the E-DMC, as described in detail in the E-DMC charter (see [Section 9.5.1](#)).

[Table 1](#) provides a brief overview of the study periods; for full details please see [SoA](#).

Table 1. Brief Overview of the Study Periods

Study Period	Days and Visits	Overview of Main Tests/Procedures
Study Eligibility Assessment	Screening (Visit 1)	Inclusion and Exclusion criteria review.
	Baseline (Visit 2)	Inclusion and Exclusion criteria review, including NAb results; Efficacy assessments; Muscle biopsy;* Obtain weight measurement; Randomization and request IP.
IP Administration	Day 1 (Visit 3)	Pre-dose Inclusion and Exclusion criteria review, including NAb results; Year 1 IP administration;
Post IP safety monitoring	Day 2 (Visit 4) to Day 34 (Visit 13)	Post-dose safety monitoring; Viral vector shedding.
Completion of Year 1	Day 60 (Visit 14) to Day 360 (Visit 19)	Routine safety monitoring; Efficacy assessments; Muscle biopsy (Day 360);* Obtain weight measurement (Visit 18);** Request IP on Day 328 (Visit 18); Viral vector shedding.
Eligibility Assessment for Year 2 IP Administration	Day 360 (Visit 19)	Assess eligibility for Year 2 IP administration, including NAb results. Viral vector shedding.
IP Administration	Day 390 (Visit 20)	Pre-dose review of eligibility for Year 2 IP administration, including NAb results; Year 2 IP administration.
Post IP safety monitoring	Day 391 (Visit 21) to Day 423 (Visit 30)	Post-dose safety monitoring; Viral vector shedding.
Completion of Year 2	Day 449 (Visit 31) to Day 749 (Visit 35)	Routine safety monitoring; Efficacy assessments; Viral vector shedding.
Long-Term Follow-up Year 3 to Year 6	Day 930 (Visit 36) to Day 2190 (Visit 43)	Routine safety monitoring; Efficacy assessments; Viral vector shedding; Muscle biopsy (Day 1830).*

Table 1. Brief Overview of the Study Periods

Study Period	Days and Visits	Overview of Main Tests/Procedures
--------------	-----------------	-----------------------------------

* First ~15 participants (with the potential to collect a maximum of 33 if needed) from selected sites. The post-Baseline muscle biopsies will be performed on Day 360 and Day 1830.

** For participants who undergo Day 328 (Visit 18) during a study dosing pause, the amount of IP to be shipped to the site will be determined once the study has been restarted. Therefore, the weight collected at Day 328 (Visit 18) will not be entered into the interactive response technology drug management system during the study dosing pause. Participants will be evaluated for Year 2 IP eligibility when the study is restarted.

The primary analysis will occur after at least 90 FAS participants complete Day 360 (Visit 19) or discontinued from the study prior to Week 52 if they had received Year 1 IP at least one year prior to the data cutoff. After the database has been released for the primary analysis, the study may become fully unblinded.

Investigators in Japan should see [Section 10.10 \(Appendix 10\)](#) for details on the interval between IP administration for consecutive participants.

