4.2. Scientific Rationale for Study Design

4.2.1. Rationale for Inclusion of a Placebo Control Group

The purpose of this Phase 3 study is to evaluate the safety and efficacy of a single IV administration of fordadistrogene movaparvovec compared to placebo in participants with DMD. The results of this study will be used to support submission for registration of this therapy for treatment of DMD. There are several reasons that a placebo-controlled design is necessary to generate robust results. First, there is considerable variability in the disease progression and therefore improved function among treated participants can be attributed to fordadistrogene movaparvovec only when compared to participants randomized to placebo. Second, in the age range of the study population, some young participants may be improving their motor function as a result of ongoing development and the only way to differentiate this improvement from that which may occur as a result of fordadistrogene movaparvovec is by comparison to a placebo group. Third, there are not adequate data on the impact of small changes in glucocorticoid regimen, as are allowed in this study, to differentiate this effect from that of fordadistrogene movaparvovec. Ensuring that the study remains blinded through the primary analysis is important because knowledge of treatment assignment can bias performance and evaluation of functional assessments.

Those randomized to Cohort 2 will receive fordadistrogene movaparvovec after completing the first year of observation, provided they remain eligible. This will enable all eligible participants to receive treatment with fordadistrogene movaparvovec.

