9.2. Sample Size Determination

A sufficient number of participants will be screened to achieve a total of approximately 99 participants in the FAS (see Section 9.3). Participants will be randomly assigned in a 2:1 fashion to Cohort 1 (approximately 66 participants) or Cohort 2 (approximately 33 participants) across the two strata (age <6 years and age \geq 6 years). This sample size is based on the primary efficacy endpoint of change from Baseline at Week 52 in the NSAA total score. The above sample size (assuming 3 participants will drop out of the study prior to Week 52) will provide 98% power to detect a treatment difference (fordadistrogene movaparvovec – placebo) of 3.0. These calculations are based on $\alpha=0.05$ (two-sided), a common standard deviation of 3.5 and using the normal approximation of the test statistic for the comparison between two means. Assuming both interim analyses will be performed (3 looks) and a gamma family alpha-spending function with gamma parameter -1 for efficacy will be used to control Type I error, the probability of crossing the boundary at the first interim analysis is 38%, at the second interim analysis is 78%, and at the primary analysis is 97%. A gamma family spending function with gamma parameter -4 will be used for the non-blinding futility boundary.

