9.3. Populations for Analysis

For purposes of analysis, the following populations are defined:

Population	Description
Enrolled	All participants who sign the Informed Consent Document.
Randomly assigned to investigational product	All participants, excluding siblings, who were randomly assigned to Cohort 1 (initially fordadistrogene movaparvovec) or Cohort 2 (initially placebo).
Full Analysis Set (FAS) (through Week 52) ^a	All participants, excluding siblings and those meeting exclusion criterion 15, who were randomly assigned and received a single dose of IP on Day 1 (Year 1 Day 1). Participants will be analyzed according to the cohort to which they were randomized.
Safety Analysis Set (through Week 52)	All participants, including siblings and those meeting exclusion criterion 15, who were randomly assigned and received a single dose of IP on Day 1 (Year 1 Day 1). Participants will be analyzed according to the IP they actually received.
Efficacy Analysis Set (long-term)	All participants, including siblings, but excluding those meeting protocol exclusion criteria 15, who received a single dose of fordadistrogene movaparvovec (either at Year 1 or Year 2).
Safety Analysis Set (Cohort 2 delayed treatment)	All participants, including siblings, who received a single dose of fordadistrogene movaparvovec on Day 390 (Year 2 Day 1).
Safety Analysis Set (long-term)	All participants, including siblings and those meeting exclusion criterion 15, who received a single dose of fordadistrogene movaparvovec (either at Year 1 or Year 2).

^a Of note, per the PCD definition in Sections 4.1 and 9.5, the primary analysis will occur after at least 90 FAS participants complete Day 360 (Visit 19) or discontinue from the study prior to Week 52 if they had received Year 1 IP at least one year prior to the data cutoff.

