Before any interim analysis is implemented, the details of the objectives, decision criteria (based on the actual number of participants and the number of looks), dissemination plan, method of maintaining the study blind, and analysis details will be recorded in the appropriate study documents. The interim analysis/analyses will be performed by an independent team of statisticians and programmers, and the results will be unblinded only to the E-DMC and/or a limited number of individuals within the Sponsor organization who are not involved in the conduct or further analysis of the ongoing study. These unblinded individuals from the Sponsor organization will be responsible for reviewing the results from the interim analyses and making a recommendation on pursuing a regulatory submission based on the interim analysis results.

The timing of public disclosure of the results of either interim analysis will be at the discretion of the Sponsor. If disclosure of interim analysis results prior to completion of the C3391003 trial is believed to have the potential to interfere with study completion, the Sponsor may choose to delay disclosure of the interim analysis until the trial has completed.

Irrespective of whether an interim analysis has been conducted, the primary analysis will occur after at least 90 FAS participants complete Day 360 (Visit 19) or discontinue from the study prior to Week 52, if they had received Year 1 IP at least one year prior to the data cutoff. . After the database has been released for the primary analysis, the study may become fully unblinded. If either an interim analysis is performed and the objectives are not met, the nominal type I error for the primary analysis will be adjusted accordingly. If either interim analysis is performed and the objective is met, the primary analysis at Week 52 will primarily be used to provide a more precise estimate of the treatment difference for the primary endpoint.

Additional analyses may be performed after the primary analysis, as needed, per regulatory requirements or in support of publications.

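### The protocol permits full unblinding after a primary analysis triggered at 90 of about 99 FAS participants, without keeping the blind for dosed boys who have not yet had their Week 52 visit

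*Protocol*

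**What the plan says.** Section 9.2 sets the target: "A sufficient number of participants will be screened to achieve a total of approximately 99 participants in the FAS", about 66 in Cohort 1 and 33 in Cohort 2. Section 4.1, the footnote in Section 9.3 and Section 9.5 place the primary analysis at the point where at least 90 FAS participants have completed Day 360 (Visit 19) or left the study before Week 52. A boy who left counts only "if they had received Year 1 IP at least one year prior to the data cutoff".

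Sections 4.1 and 9.5 then both state: "After the database has been released for the primary analysis, the study may become fully unblinded".

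Section 9.3 defines the FAS as all participants randomised and dosed on Day 1, apart from siblings and those meeting exclusion criterion 15. It is not restricted to the boys who make up the trigger of 90. Section 9.5 leaves room for further analyses after the primary one.

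On why the blind matters, Section 4.2.1 says that "knowledge of treatment assignment can bias performance and evaluation of functional assessments". The same sentence commits to blinding through the primary analysis. It does not commit to blinding through each participant's own Week 52 visit.

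**The concern.** The gap between 90 and about 99 means that some dosed FAS boys may still be waiting for Visit 19 when the database is released. The protocol then allows their allocation to be disclosed, and no text reviewed holds it back from the boy, his caregiver, the site or the clinical evaluator until he has been tested.

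The assessments exposed are the ones the protocol protects most carefully. The NSAA is scored item by item by a clinical evaluator, and two of its items supply the 10-metre and rise-from-floor times, whose velocities come first among the gated secondary endpoints in Section 9.1. Section 8.1.1 provides for video review only to give evaluators feedback, not to score participants, so no blinded rescore is planned for a test done with allocation known. Section 6.3.3 withholds CK, AST/ALT, antibody and biopsy results and tries to keep evaluators away from records that could reveal allocation. Full unblinding before a boy's Week 52 visit would undo those measures for him.

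What is at stake is any later Week 52 estimate that uses the whole FAS, because it would mix blinded and open assessments of functional endpoints.

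**Working it through.** **1. The plan's own figures.** Inputs from Section 9.2: difference 3.0, SD 3.5, two-sided α = 0.05, 2:1 allocation, about 99 in the FAS with 3 dropouts. With SE = SD × √(1/n₁ + 1/n₂) and power = Φ(3.0/SE − 1.96):

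- 99 boys (66 + 33): SE = 3.5 × √(1/66 + 1/33) = 0.746; power 98.0%.
- 96 boys (64 + 32): SE = 3.5 × √(1/64 + 1/32) = 0.758; power 97.7%. The stated 98% is reproduced.
- 90 boys (60 + 30): SE = 3.5 × √(1/60 + 1/30) = 0.783; power 97.0%. The more than 95% given in the amendment rationale is confirmed. With both interim analyses at 30 and 60, gamma (−1) spending and a final look at 90, power is 96.1%.

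These figures show only that the trigger at 90 is adequately powered. They do not measure the unblinding problem.

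**2. Maximum number exposed.** 99 − 90 = 9, which is 9/99 = 9.1% of the FAS; at 2:1, about 6 in Cohort 1 and 3 in Cohort 2. Both 99 and 90 are soft: the target is approximate and the trigger is a minimum.

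**3. Number plausibly exposed.** Unblinding follows database release, not the 90th boy's visit. Let r be the rate at which the last boys reach Week 52 and L the lag from trigger to unblinding. The protocol gives neither. Exposed = max(0, 9 − r × L). Assuming L = 8 weeks:

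| r (boys per week) | r × L | Exposed |
|---|---|---|
| 0.25 | 2 | 7 |
| 0.5 | 4 | 5 |
| 1 | 8 | 1 |
| 2 | 16 | 0 |

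With no lag, or with a long gap before the last boys' visits, the figure is 9.

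**4. Effect on the primary test.** The order is data cutoff, database release, then possible unblinding. A Week 52 score taken after unblinding is not in the released database, so the shift in the primary estimate is 0.

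**5. Effect on a later full-FAS estimate.** Let knowledge of allocation shift the late boys' scores by b₁ in Cohort 1 and b₂ in Cohort 2, and let B = b₁ − b₂. In a simple difference of means the shift is (6/66) × b₁ − (3/33) × b₂ = (1/11) × B = 0.09 × B. So B = 1 NSAA point shifts the estimate by about 0.09 and B = 3 points by about 0.27, against a planned difference of 3.0. With only 5 boys exposed in the same 2:1 ratio, the shift is 5/99 = 0.05 per point. The size of B is not known.

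**The case against.** The strongest reply is that the protocol grants a permission and does not announce a plan. Unblinding is optional, it follows release, and the trigger is a minimum, so it may be that no boy is tested open. The confirmatory result is safe in every case. Section 4.2.1 promises blinding through the primary analysis, and that promise is kept. Section 6.3.3 gives evaluators some protection. A later full-FAS analysis is only a possibility, its data handling can sit in the SAP (not available for this review), and the effect per point of bias is small.

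Most of this stands, and it rules out several readings that a reader might otherwise infer:

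- That the last 9 boys will be assessed unblinded. Nine is a ceiling.
- That the primary test is biased. Step 4 shows it is not.
- That about 9% of the sample cannot give a blinded primary endpoint. Some or all may have Visit 19 before release, and earlier blinded visits can enter the repeated-measures model in any case.
- That Section 4.2.1 is contradicted. It is not.
- That the loss is the wider interval or lower power from analysing 90 rather than 99. That is a separate choice, and power remains 97.0%.

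One part of the reply does not stand. Who stays blinded and until when is trial conduct. The protocol grants the permission, so the protocol is the place to limit it. A count near 9 is also not far-fetched: Section 5.3 foresees operational pauses long enough for the interval from screening to dosing to exceed 90 days, and Section 4.1 allows enrolment of an over-represented age stratum to be paused. Either could leave the last boys well behind the 90th.

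**Conclusion.** The point holds as a cheap improvement to trial conduct, not as a flaw in the confirmatory analysis. Sections 4.1 and 9.5 allow full unblinding while up to about 9 dosed FAS boys may still be waiting for Week 52, and no text reviewed protects their blind until then. The range is 0 to about 9. The possible harm is confined to later Week 52 estimates that include those boys: about 0.09 NSAA points per point of differential bias. This assumes that all 9 are exposed, that they split 2:1, and that the estimate behaves like a difference of means.

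A reader might extend the point to interim results, since Section 9.5 says only that "the Sponsor may choose to delay disclosure of the interim analysis until the trial has completed". The documents do not support that extension. Interim disclosure would concern aggregate results, whereas the bias described in Section 4.2.1 comes from knowing individual assignment. Section 9.5 also limits who sees unblinded interim results and requires a dissemination plan and a method of maintaining the blind to be recorded beforehand. Whether delay should be mandatory is a debatable trade-off, and that wording need not change.

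**What to change.** In Sections 4.1 and 9.5, qualify the unblinding sentence along these lines: after database release for the primary analysis, blinding of the participant, caregiver, site staff and clinical evaluator is maintained for each FAS participant until his own Visit 19 assessments are complete; individual allocations from the primary analysis stay behind a firewall until then; any Week 52 data collected after a participant has been unblinded are flagged in later analyses.

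The cost is amendment wording, a temporary firewall, and later release of allocations for the last few boys. Sample size, power and the trigger at 90 are unchanged. With the change in place, the number of FAS boys whose Week 52 assessment is exposed by release of the primary analysis falls from at most about 9 to 0.

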4.2. Scientific Rationale for Study Design

4.2.1. Rationale for Inclusion of a Placebo Control Group

The purpose of this Phase 3 study is to evaluate the safety and efficacy of a single IV administration of fordadistrogene movaparvovec compared to placebo in participants with DMD. The results of this study will be used to support submission for registration of this therapy for treatment of DMD. There are several reasons that a placebo-controlled design is necessary to generate robust results. First, there is considerable variability in the disease progression and therefore improved function among treated participants can be attributed to fordadistrogene movaparvovec only when compared to participants randomized to placebo. Second, in the age range of the study population, some young participants may be improving their motor function as a result of ongoing development and the only way to differentiate this improvement from that which may occur as a result of fordadistrogene movaparvovec is by comparison to a placebo group. Third, there are not adequate data on the impact of small changes in glucocorticoid regimen, as are allowed in this study, to differentiate this effect from that of fordadistrogene movaparvovec. Ensuring that the study remains blinded through the primary analysis is important because knowledge of treatment assignment can bias performance and evaluation of functional assessments.

Those randomized to Cohort 2 will receive fordadistrogene movaparvovec after completing the first year of observation, provided they remain eligible. This will enable all eligible participants to receive treatment with fordadistrogene movaparvovec.

